**REVISION HISTORY**

Ver.	Date	Summary of Changes
1.0	05 JUL 2016	Original Version
2.0	13 JAN 2017	Increased time permitted between baseline and surgery from 30 days to 90 days.
3.0	12 JUL 2017	Moved comparison of pre- and post-op alignment from a secondary effectiveness endpoint to a primary effectiveness endpoint to address study design considerations.
3.1	18 SEP 2017	Added clarification to state that post-operative alignment outcomes will be compared to surgeon's pre-operative alignment goals versus neutral alignment.
4.0	24 OCT 2017	Increased subject follow-up time from 3 months to a minimum of 6 months and a maximum of 12 months. Clarified that all patients with AEs at the final study visit (6M or 12M) will be followed until AE resolution or termination of study. Added clarification for patients who are to be excluded under Exclusion Criterion 'c'. Added Change Summary table after title page.
5.0	07 DEC 2018	Update contact information. Corrected footnote (b) under the Schedule of Procedures to reflect standard of care pre-operative and post-operative blood work.
6.0	09 SEP 2019	Add Continued Access arm to study design. Update Sections 1.0, 5.0, 5.1, 5.2, 6.5, 7.0, 7.1, 7.3, 7.4, 7.5, 7.6, 7.7, 9.1, 9.2, 9.3 and 15.0 to clarify requirements for Continued Access arm. Add Table 3 with Schedule of Procedures for Continued Access arm. Update MCRA CRO address in Section 16.0. Add administrative clarification regarding treatment of patients that withdraw consent or are withdrawn by the PI before surgery in Section 6.5. Add administrative clarification regarding data collection requirements for Unscheduled Visits in Section 7.8. Add administrative clarifications regarding Adverse Event follow up requirements in Schedule of Procedures (Tables 2 and 3) and Sections 8.1, 10.2 and 10.8. Add administrative clarifications regarding stopping rules for safety concerns in Sections 8.5 and 10.7.

**1. STUDY SUMMARY**

Title	TSolution One Total Knee Arthroplasty Clinical Trial
Sponsor	THINK Surgical, Inc.
Short Title	TSolution One TKA
Protocol Number	16-PROTO-01
Lead Investigator	[name]
Methodology	Multi-center, prospective, non-randomized clinical trial
Study Type	Observational
Study Duration	Patients will be consented to participate for a period of no less than 6 months and no more than 12 months. Each study arm will terminate once the last enrolled patient of the study arm completes their 6 month study visit. Patients who are not expected to reach their 12 month visit prior to study arm termination will be exited at 6 months; all others will be exited at 12 months.
Objectives	The goal of this study is to evaluate the safety and effectiveness of robotic-assisted total knee arthroplasty, and to document clinical and radiological outcomes for TCAT-assisted implantation using the TSolution One System for TKA compared to a literature control.
Diagnosis and Main Inclusion Criteria	Primary osteoarthritis of the knee requiring a primary unilateral total knee arthroplasty (TKA)
Number of Patients	IDE Study Arm: The total sample size to be enrolled is 115 patients (103 patients plus 10% for possible loss to follow-up).  Continued Access Arm: Once the IDE enrollment is completed, up to 50 patients will be enrolled in a separate arm of the study (Continued Access arm).

Outcome Measurements	
Primary Effectiveness Endpoint - The primary effectiveness endpoint is alignment of coronal mechanical axis at 3 months defined as achieving varus-valgus alignment less than <math>\pm 3^\circ</math> in the frontal plane after TKA. A review of 1,376 patients undergoing conventional TKA with manual instrumentation showed a 32% malalignment for mechanical axis greater than <math>3^\circ</math> (Mason). This study is designed to demonstrate that the investigational device is capable of reducing the malalignment rate by 50%, that is, to 16%.
 
Primary Safety Endpoint - The primary safety endpoint is a composite safety endpoint that includes a number of relevant adverse events identified in a literature search, each having an expected incidence <math>\leq 2.7\%</math>. The sum of these relatively rare complications is equal to 7.6%. The percentage of patients with TCAT-assisted implantation using the TSolution One System for TKA experiencing the composite safety event will be compared to 7.6%.
 
Secondary Safety Endpoints
 
 
• Bleeding complications are not rare and will be assessed separately as a secondary safety endpoint based on the incidence of transfusions (allogeneic or autologous).
 
• Complications related to excessive bleeding that require surgical intervention will be assessed and summarized as a subset of the bleeding complications above.
 
• Other secondary safety endpoints include the incidence of the individual adverse events comprising the composite.
 
 
Secondary Effectiveness Endpoints
 
Effectiveness endpoints are considered secondary for this study and are summarized below:
 
 
• Postoperative function will be evaluated by collecting Knee Society Scores at 3, 6, and 12 (if available) months.
 
• Health related quality-of-life will be assessed by collecting Short Form 12 (SF-12) Health Survey scores at 3, 6, and 12 (if available) months.
 
• Post-operative alignment outcomes will be compared to pre-operative alignment goals at 3 months.
 

Success/Failure Criteria	
The study success criterion is to simultaneously demonstrate that the malalignment rate is less than or equal to 0.16 (effectiveness endpoint) and that the composite safety event rate is less than 0.136 (safety endpoint) based on one-sided exact binomial tests with type 1 error rate equal to 0.05. A p-value <math>\leq 0.05</math> for both tests will indicate study success.

Hypotheses	
IDE Study Arm
 
The primary effectiveness hypothesis for this study is that the probability of malalignment for patients undergoing TCAT-assisted implantation using the TSolution One System for TKA is 50% smaller than the reference rate of 32%, that is, less than or equal to 16%.
 
H0: <math>\pi_i \geq 0.16</math> (50% of reference rate = 32%)  HA: <math>\pi_i < 0.16</math>
 
In this formulation, <math>\pi_i</math> is the true malalignment probability for the investigational device.
 
A one-sided type 1 error of <math>\alpha=0.05</math> was assumed. Using industry standard software (nQuery Advisor 7.0, Module POT0x-1), it was determined that statistical power to reject the null hypothesis in favor of the alternative hypothesis is equal to 89.3% with a sample size of N=103 patients if the true malalignment rate is 0.07.
 
The primary safety hypothesis for this study is that the probability of experiencing the composite safety endpoint for patients undergoing TCAT-assisted implantation using the TSolution One System for TKA is not clinically significantly elevated relative to the historic control value of 7.6% for manual TKA. Symbolically, the primary safety hypotheses regarding non-inferiority relative to historical control may be represented as follows:
 
H0: <math>\pi_i \geq \pi_c + \delta</math> (clinically inferior safety)  HA: <math>\pi_i < \pi_c + \delta</math> (not clinically inferior safety)
 
In this formulation, <math>\pi_i</math> and <math>\pi_c</math> are the true event rates when using the investigational device and manual TKA, respectively. As noted above, based on a literature review, <math>\pi_c = 0.076</math>. A non-inferiority margin of 0.06 was selected. Therefore, these hypotheses reduce to:
 
H0: <math>\pi_{\text{composite}} \geq 0.076 + 0.06 = 0.136</math>  HA: <math>\pi_{\text{composite}} < 0.076 + 0.06 = 0.136</math>
 
A one-sided type 1 error of <math>\alpha=0.05</math> was assumed. Using industry standard software (nQuery Advisor 7.0, Module POT0x-1), it was determined that statistical power to reject the non-inferiority hypothesis was equal to 82.5% with a sample size of N=103 patients.
 
Continued Access Study Arm
 
There will be no formal hypothesis testing with the Continued Access Arm of the study. Patients will be followed for safety and to gain additional information on device use, therefore, no power analysis has been performed to estimate sample size. The Continued Access Arm will enroll up to 50 patients.

------------	--


Statistical Methodology
	
Demographic, baseline, peri-operative and postoperative characteristics for all recruited cases will be assessed from data which is collected on the relevant case report forms. Continuous variables included in demographic, baseline, peri-operative and postoperative summaries, will be evaluated using descriptive statistics (N, mean, median, standard deviation, minimum, and maximum). Dichotomous and polychotomous variables included in demographic, baseline, peri-operative and postoperative summaries, will be described as frequencies and percentages at each level of the categorical variable.
 
The primary effectiveness and safety hypotheses will be tested using exact tests for a single proportion with one-sided type 1 error rate set to <math>\alpha=0.05</math>. The study success criterion requires rejection of both the effectiveness and safety null hypotheses.
 
The primary effectiveness endpoint, the safety endpoint and all secondary endpoints including bleeding and the individual components of the composite safety endpoint, will each be summarized by counts, percentages, and the upper bounds of one-sided 95% exact binomial confidence intervals (CI). Patient function and health related quality-of-life will be described by summarizing baseline, 3-month, 6 month, 12 month (if available) and change scores at each time point in the Knee Society Scores and SF-12 Health Survey Physical and Mental Health Composite Scores (PCS & MCS), using descriptive statistics including mean, standard deviation, median, minimum, and maximum. The ITT analysis set will be used in primary analyses. Specific analyses may be repeated in a Per Protocol analysis set that requires completion of the index procedure and no clinically significant protocol violations.
 
Continued Access Study Arm
 
The continued access study arm will not include any hypothesis testing and will not be part of the primary or secondary endpoint analysis. Data from the continued access arm will be provided as descriptive statistics, which can include counts, percentages, mean, standard deviation, median, minimum, and maximum and the upper bounds of one-sided 95% exact binomial confidence intervals (CI). This will include an analysis of safety, patient function, and health related quality-of-life data described by summarizing baseline, 6 week, 3-month, 6 month, 12 month (if available) and change scores at each time point, as applicable.

--------------------------------	--

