**$H_0: \pi_i \geq \pi_c + \delta$  (clinically inferior safety)**

**$H_A: \pi_i < \pi_c + \delta$  (not clinically inferior safety)**

In this formulation,  $\pi_i$  and  $\pi_c$  are the true event rates when using the investigational device and manual TKA, respectively. As noted above, based on a literature review,  $\pi_c = 0.076$ . A non-inferiority margin of 0.06 was selected. Therefore, these hypotheses reduce to:

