**$H_0: \pi_{\text{composite}} \geq 0.076 + 0.06 = 0.136$**

**$H_A: \pi_{\text{composite}} < 0.076 + 0.06 = 0.136$**

A one-sided Fisher's exact test will be used to test the primary safety hypothesis that the composite safety event rate is larger than historical control (0.076) plus the non-inferiority margin of  $\delta=0.06$ . That is, the null hypothesis is that the investigational device event rate is 0.136 or larger and the alternative hypothesis is that this event is less than 0.136. Based on the Sponsor's expectation that the technology is associated with improved outcomes, it was assumed for the purpose of sample size determination that that composite safety event rate for patients undergoing primary TKA with femoral and tibial preparation by the TSolution One™ Surgical System is 20% smaller than control, or equal to 0.0608. A one-sided type 1 error of  $\alpha=0.05$  was

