#### THINK Surgical, Inc.

Proprietary rights of THINK Surgical, Inc. are involved in the subject matter of this material. It is submitted in confidence for a specific purpose and the recipient by accepting this material agrees that it will not be used other than for the express purpose for which it was delivered.

Disclosure to others without written permission from THINK Surgical, Inc. is forbidden.

assumed. Using industry standard software (nQuery Advisor 7.0, Module POT0x-1), it was determined that statistical power to reject the non-inferiority hypothesis was equal to 82.5% with a sample size of N=103. Because of the discreteness of the exact binomial distribution, the power curve is not monotonic. Power for sample sizes of N=102, 103, 104, 105, 106, 107, 108, 109, 110, 111, 112, 113, 114, 115, 116, 117, 118, 119, 120, 121 and 122 are 71.9%, 82.5%, 81.8%, 81.1%, 80.3%, 79.6%, 78.9%, 78.1%, 77.3%, 76.6%, 75.8%, 84.9%, 84.3%, 83.7%, 83.1%, 82.5%, 81.8%, 81.1%, 80.5%, 79.8%, and 87.6%. The smallest sample size with power  $\geq 80\%$  is 103. For sample sizes of N=103 and above, power never falls below 75.8%. The minimum sample size for which power remains at least equal to 80% at that value for all larger values is N=113.

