**$H_0: \pi_i \geq 0.16$  (50% of reference rate = 32%)**

**$H_A: \pi_i < 0.16$**

In this formulation,  $\pi_i$  is the true malalignment probability for the investigational device.

A one-sided type 1 error of  $\alpha=0.05$  was assumed. Using industry standard software (nQuery Advisor 7.0, Module POT0x-1), it was determined that statistical power to reject the null hypothesis in favor of the alternative hypothesis is equal to 89.3% with a sample size of N=103

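### Section 9.1 gives the wrong sample size for sustained 80% safety power (N=113 should be N=122), and no power is stated for the joint success criterion, about 74% at N=103 if the endpoints are independent

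*Combined protocol and SAP*

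**What the plan says.** The success rule is joint. The Success/Failure Criteria row of Section 1 requires the effectiveness and safety results to be shown simultaneously, "based on one-sided exact binomial tests with type 1 error rate equal to 0.05", with a p-value of 0.05 or less on both. The Statistical Methodology row repeats it: "The study success criterion requires rejection of both the effectiveness and safety null hypotheses".

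Power is given one test at a time.

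- **Safety (Section 9.1; also Section 1, Hypotheses):** "statistical power to reject the non-inferiority hypothesis was equal to 82.5% with a sample size of N=103". Section 9.1 lists safety power for each N from 102 to 122, names 103 as the smallest N with power of at least 80%, and adds: "The minimum sample size for which power remains at least equal to 80% at that value for all larger values is N=113".
- **Effectiveness (Section 9.2; also Section 1, Hypotheses):** power is "equal to 89.3% with a sample size of N=103" if the true malalignment rate is 0.07, and stays above 80% from N=95.

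Enrolment is 115, meant to leave 103 after 10% loss. No section gives the probability that both tests reject, or says anything about dependence between the two outcomes.

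**The concern.** There are two separate problems.

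The first is internal. The N=113 statement covers all larger sample sizes, and the list just before it contains a larger size below 80%. It can be seen to be wrong without any calculation.

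The second is an omission. The 80% benchmark that picks out N=103 belongs to the safety test, but the trial succeeds only if the effectiveness test rejects as well. The chance of meeting both cannot exceed the smaller of the two powers and is usually below it. The plan therefore does not tell its readers how likely the design is to meet its own criterion at the rates it assumes. Type 1 error is not at issue: requiring both tests to reject does not inflate it. Only power is affected.

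**Working it through.** **Inputs, all from the plan**

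- Each test is a one-sided exact binomial test at 0.05 (Section 1, Success/Failure Criteria).
- Safety null: "the null hypothesis is that the investigational device event rate is 0.136 or larger" (Section 9.1), from 0.076 + 0.06; "A non-inferiority margin of 0.06 was selected".
- Safety assumed true rate: "20% smaller than control, or equal to 0.0608" (Section 9.1).
- Effectiveness null 0.16, assumed true rate 0.07 (Section 9.2).
- N=103 evaluable, 115 enrolled (Section 9.1); 115 × 0.90 = 103.5.

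**Method.** The critical count c is the largest value with P(X ≤ c | N, null rate) ≤ 0.05. Power is P(X ≤ c | N, assumed rate).

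**Step 1: reproduce the stated powers at N=103**

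| Test | c | Attained alpha | Power | Plan |
|---|---|---|---|---|
| Safety | 8 | 0.0494 | 82.52% | 82.5% |
| Effectiveness | 10 | 0.0476 | 89.38% | 89.3% |

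All 21 safety powers listed in Section 9.1 reproduce to within 0.1 point, as does the upper bound of 0.1358 for 8 of 103. The method and inputs are therefore those of the plan.

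**Step 2: the N=113 statement.** The list starts at N=102, so N=121 is its twentieth entry, printed as 79.8%; I compute 79.84% (c=9). At N=122, c rises to 10 and power is 87.6%. From N=103 up to 1,499, safety power is below 80% only at N=107 to 112 and at N=121. The smallest N from which it stays at or above 80% is therefore 122.

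**Step 3: joint power under independence, same N for both endpoints.** Joint power = safety power × effectiveness power. At N=103: 0.8252 × 0.8938 = 0.738.

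| N | Safety | Effectiveness | Joint |
|---|---|---|---|
| 103 | 82.5% | 89.4% | 73.8% |
| 110 | 77.4% | 85.2% | 66.0% (lowest in 103–115) |
| 113 | 85.0% | 90.2% | 76.7% (highest in 103–115) |
| 115 | 83.8% | 89.2% | 74.8% |
| 122 | 87.6% | 91.4% | 80.1% (first at or above 80%) |

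**Step 4: what dependence can do.** For any dependence, joint power lies between (safety + effectiveness − 1) and the smaller of the two. At N=103:

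- lower bound: 0.8252 + 0.8938 − 1 = 0.719;
- upper bound: 0.8252, or 82.5%.

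At N=107 to 112 safety power alone is 79.6% down to 75.8% in the plan's own list, so joint power is below 80% at those six sizes under any dependence.

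Exact joint binomial calculations with a patient-level correlation phi between the two outcomes give:

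| phi | N=103 | Highest in 103–115 (N=113) |
|---|---|---|
| 0 | 73.8% | 76.7% |
| 0.3 | 75.6% | 78.3% |
| 0.5 | 77.1% | 79.6% |
| 0.6 | 77.9% | 80.4% |

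**Step 5: other sensitivities**

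- *Unequal evaluable N.* With safety N from 103 to 115 and effectiveness N from 95 to 115, the highest joint power under independence is 77.5%.
- *Margin.* Section 5.2 gives a margin of 7.0%, in conflict with 0.06 in Sections 1 and 9.1; the stated powers reproduce with 0.06. With a null of 0.146, joint power under independence is unchanged at N=103 (73.8%) but is 81.1% to 82.7% at N=113 to 115.
- *Safety rate.* If the true rate were the control value of 7.6%, safety power at N=103 would be 61.8% and joint power 0.618 × 0.894, about 55%.

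**The case against.** The plan's single-test powers are correct, correctly labelled and reproducible. The 80% benchmark sits under a heading about the safety endpoint and is not presented as power for overall success. Powering each co-primary test separately is a reporting choice, and a reader who sees the joint rule can multiply the two figures. All of that stands, and it makes the second point an omission, not an arithmetic error.

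The independence assumption and the common N are mine, not the sponsor's. Safety is analysed in the ITT set (Section 9.3), while effectiveness needs a 3-month long-leg film, so the denominators may differ. The 66% figure needs exactly 110 patients evaluable on both endpoints; 103 and 115 give 73.8% and 74.8%. Section 9.1 itself warns that the safety power curve is not monotonic and prints its dips.

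The N=121 shortfall is 0.2 points, at a size above planned enrolment and with the correct figure printed beside it. It changes no decision, but the sentence is still false as written.

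Two stronger readings are tempting:

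- *That joint power never reaches 80% for N=103 to 115.* A reader might infer this from the independence figures, but it is not an absolute bound. The upper bound is 82.5% at N=103 and 85.0% at N=113, a correlation of about 0.6 takes N=113 past 80%, and the result also depends on the 0.06 margin.
- *That the plan presents an 80% to 90% chance of study success.* No sentence says so; each figure is tied to its own hypothesis.

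**Conclusion.** The point holds in two parts. The N=113 statement in Section 9.1 is wrong by the plan's own list and should read N=122; this needs no assumption beyond the plan's inputs. Power for the declared success criterion is not stated. At the assumed rates and the 0.06 margin it is about 74% at N=103, and 66% to 77% over N=103 to 115, given independent endpoints and the same evaluable N. Without the independence assumption, what can be said is 71.9% to 82.5% at N=103, and below 80% at N=107 to 112. The validity of a success claim, the critical counts and type 1 error are unaffected.

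**What to change.** 1. In Section 9.1, change N=113 to N=122 in the sentence on the smallest sample size from which safety power stays at or above 80%.
2. In Section 9 and in the Hypotheses row of Section 1, add a statement along these lines: *Study success requires both tests to reject. At true rates of 6.08% (safety) and 7% (malalignment), and assuming independent endpoints with the same number of evaluable patients, the power to meet both is about 74% at N=103 (71.9% to 82.5% under any dependence) and ranges from 66% to 77% for 103 to 115 evaluable patients.*
3. Make clear that the 80% benchmark used to select N=103 refers to the safety test alone.
4. These figures use the 0.06 margin, so reconcile Section 5.2 with Sections 1 and 9.1; if the margin changes, recompute them.

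Items 1 to 3 are text only. Enrolment, tests and thresholds do not change. The one downside is that the stated power for success is less favourable than either single-test figure.

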## 2. INTRODUCTION

### 2.1. Background

End-stage osteoarthritis of the knee is typically treated with total knee arthroplasty (TKA) in which the articulating surfaces of the distal femur and proximal tibia are replaced with prosthetic components. It is very successful in terms of relieving patients' pain and restoring joint function (1), (2), (3). However, the mechanical alignment of the knee after TKA and the ability to balance soft tissue play a major role in the longevity and success of the implant (4), (5), (6). It has been suggested that errors in surgical technique may be the most common reason for failure of TKAs (7), (1), (8). Thus, one of a surgeon's goals is to achieve accurate alignment of the tibial and femoral components in the frontal, sagittal, and transverse planes (9).

Manufacturers have traditionally recommended positioning the knee implant such that the "ideal" mechanical axis of the knee is restored. This mechanical axis is defined as a straight line passing through the center of the femoral head, the center of the knee joint, and the midpoint of the ankle (10), (11). Implant manufacturers have developed complex instrumentation sets to help achieve this ideal implant placement. However, every mechanical instrumentation system relies on visual inspection and the feel of a surgeon to confirm the accuracy of limb and implant alignment, and implant misalignment is still a problem. Despite a surgeon's best intentions, this results in anywhere from 15-72% of conventional TKA's having an error in mechanical axis alignment of greater than 3° (12), (13). A misalignment of greater than 3° varus-valgus has traditionally been considered the threshold past which implant longevity decreases. Several studies have suggested that if the error in varus-valgus alignment exceeds 3° after TKA, the patients are more likely to experience increased pain, poor biomechanics, reduced function, and a decreased longevity of the implants (14), (10), (15), (5). Jeffery et al. (10) has reported that the rate of loosening was 24% when mechanical axis alignment error exceeded 3° compared to only 3% when mechanical axis alignment was less than 3°. Loosening is the second leading cause for revision surgery with 24.1% of revisions being attributed to aseptic loosening (1). Thus, achieving ideal implant alignment with minimal error is essential for long term surgical success.

A variety of computer assisted navigation systems have been developed to improve alignment accuracy, and have resulted in a reduction in alignment errors (16), (17). However, although these navigation systems are successful at aligning the cutting guides, there still exists an inaccuracy that results from the cutting blocks and oscillating jigs used to prepare the bone (18), (19).

To address the issues with imprecise cutting, robotic systems were developed to combine the placement and alignment accuracy of navigation with the precision of computer controlled machining. Several systems have been developed specifically to address the implementation of TKA by accurately executing the preoperative plan (20), (21), (22), (23). The ROBODOC® Surgical System, an earlier, predicate of TSolution One that has been FDA-cleared for Total Hip Arthroplasty also has an application intended for assisted TKA. This system has been approved in

